2.8 Decimal Place Rules

2.8.1 Derived parameters

Derived parameters such as CCI require specific decimal place rules as the ones currently defined in SAP section 3 are not appropriate. Therefore, the mean, min, max, Q1 and Q3 should be rounded to 2dp, SD to 3dp.

2.8.2 Linear regression parameters

Specific rules for decimal places for the linear regression parameters are not outlined in section 3 of the SAP. So, the regression coefficient and the confidence interval should be rounded to 2dp, the p-value and SD to 3dp.

Mucus volume rules are slightly different and are specified in section 2.11.2.

2.8.2.1 Raw data exceeding 4 decimal places

In situations where the decimals places in the raw data exceed 4 decimal places then all summary statistics will be rounded to 4 decimal places
Developed from TP-BPM-WW-032; related to SOP-BPM-WW-001 D3250R00107

2.9 Covariance Structure

The following process for determining covariance structure, for the analysis of lobe dependency models, will be applied to the primary endpoint, mucus volume for the overall model in the evaluable analysis set.

This is the structure that will then be used for the rest of the analysis of lobe dependency models (section 3.2.3 of the SAP). An unstructured covariance structure should be implemented first to see if the model converges. If this fails to converge then the best fitting model from the following should be used; compound symmetry (CS), Toeplitz (toep), Variance components (VC), Heterogenous compound symmetry (CSH), Heterogenous Toeplitz (toeph), autoregressive(1) (AR(1)) and Heterogenous autoregressive(1) (ARH(1)).

To determine the best fitting model, all these structures will be tested to see if any of them converge. And that the Hessian matric is positive definite. Of the ones that converge, those with the lowest AIC value will be used in the analysis.

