Deposition in the intrathoracic and peripheral airways will be measured using drug deposition ratio before and after benralizumab treatment using lung models from high-resolution CT scans at week 0 (baseline) and week 13 (\pm 5 days). Central airway will be defined as the trachea and all airways with diameter > 1-2 mm and reaching out to 7–10th generation of dichotomous branching, while the peripheral airways will be defined as airways with a diameter < 1-2 mm and > 10 generations of branching. As detailed in the above list of relevant structural and functional FRI parameters, FRI analyses on CT scans at baseline (Visit 1) and following benralizumab treatment (at Visit 4) will be conducted on untrimmed or trimmed airways. Untrimmed analyses will include all airway branches visible at each visit, while the trimmed analysis will only include airway branches visible across both visits 1 and 4. All FRI parameters will be assessed in the different zones of the respiratory system - right upper lobe (RUL), right middle lobe (RML), right lower lobe (RLL), left upper lobe (LUL) and left lower lobe (LLL), as well as into central and distal regions, the latter two regions only for FRI parameters related to the airways (siVaw, and iVaww). Specifically, all FRI parameters related to the airways (siVaw and iVaww) will be assessed from generations 1 to 10 and reported by different zones of the respiratory system and by central and distal regions. Additionally, airway wall volume (iVaww) will be at generations 3 and 4, based on assessments planned for similar ongoing studies.

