9.4.2 Efficacy

9.4.2.1 Primary Objectives

For the primary objective, a paired *t*-test will be used to determine if there is a significant difference between the mean of untrimmed total mucus volume at TLC at week 0 vs week 13, irrespective of patient characteristics.

Secondary analysis of the primary endpoint (untrimmed total mucus volume at TLC) will be a mixed-effects model to incorporate the repeated measurements (corresponding to the different lobes) for each subject. The outcome of change from baseline in the primary endpoint at week 0 vs week 13 per lobe will be modelled in terms of a fixed effect for lobe and a patient-level random effect to estimate the heterogeneity across lobes. Adjustment will be made for baseline mucus volume per lobe. The fitted model will estimate the average change from baseline in mucus volume at week 0 vs week 13 per lobe.

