3.2.1.5 Secondary Analysis of Primary Endpoint

For the secondary analysis of the primary endpoint a mixed-effects model will be employed to incorporate the repeated mucus volume measurements (corresponding to the different lobes) for each subject. The fitted model will provide estimates of the average change from baseline in mucus volume per lobe, with lobe as a fixed effect and a patient-level random effect to estimate the heterogeneity across lobes. Adjustment will be made for the baseline value of mucus volume.

Equation 1 The mixed-effects model will be as follows:

$$y_{ij} = \beta_0 + \beta_{1j}X_{ij} + \beta_2(baseline)_{ij} + b_{0j} + \varepsilon_{ij}$$

where

• y_{ij} represents change from baseline in mucus volume for subject *i* lobe *j*

- β_0 is the intercept
- β_{1j} is the coefficient for lobe *j*, estimating the average change from baseline in mucus volume for lobe *j*
- X_{ij} is an indicator of whether the mucus volume measurement for subject *i* corresponds to lobe *j*
- β_2 is the coefficient for baseline mucus volume
- $(baseline)_{ij}$ is the baseline mucus volume value for subject *i* corresponding to lobe *j*.
- b_{0i} is the random effect for the *i*th subject
- ε_{ij} is the residual error term

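### The fallback covariance for the lobe models can depend on how the lobes are numbered, and the addendum does not say whether its structures replace or supplement the patient random effect

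*SAP*

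**What the plan says.** Protocol 9.4.2.1 describes the secondary analysis of mucus volume as a model of the per-lobe change "in terms of a fixed effect for lobe and a patient-level random effect to estimate the heterogeneity across lobes". SAP 3.2.1.5 repeats this, "with lobe as a fixed effect and a patient-level random effect to estimate the heterogeneity across lobes", and SAP 3.2.2.5 applies the same form to the secondary FRI endpoints. The planned output is the average change in each lobe.

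The lobes are those listed in protocol 8.1.1.1: RUL, RML, RLL, LUL and LLL. Neither document gives them an order, spacing or numbering for modelling.

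SAP Addendum 2.9 then adds a covariance rule. The first step is: "An unstructured covariance structure should be implemented first to see if the model converges". If it fails, seven structures are tried: CS, TOEP, VC, CSH, TOEPH, AR(1) and ARH(1), with a check that the Hessian is positive definite. The choice is by AIC: "Of the ones that converge, those with the lowest AIC value will be used in the analysis". The selection is made once, on mucus volume in the evaluable set.

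The addendum does not withdraw the patient random effect. It does not say whether the structure is for the residual matrix or the random-effect matrix. The SAP section it cites for the lobe models (3.2.3) is the baseline correlation analysis, so the link to 3.2.1.5 and 3.2.2.5 has to be inferred.

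**The concern.** There are two separate problems.

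- AR(1), ARH(1), TOEP and TOEPH let the correlation between two lobes depend on how far apart they stand in a list. For visits in time that is meaningful. For five anatomical lobes it depends on the coding, so a prespecified AIC rule can select a different structure, and give different standard errors, after a relabelling that carries no information.
- If the listed structures are added to the patient random intercept, some of them already contain everything the intercept can contribute. The likelihood is then flat in one direction. The preferred unstructured model is one of these, so the plan makes it more likely that its own first choice fails and that the fallback is reached.

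At stake is the reproducibility of the secondary per-lobe estimates and their standard errors.

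**Working it through.** The plan gives no figure on this point, so there is nothing to reproduce. The check is structural, with a simulation as illustration.

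**Inputs.** Five lobes (protocol 8.1.1.1); the structures and the AIC rule (Addendum 2.9); the patient random effect (SAP 3.2.1.5, protocol 9.4.2.1); 34 evaluable participants (protocol 1.1), used only to size the simulation.

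**Step 1: which matrix.** A single random intercept has a 1×1 covariance matrix, for which the listed structures coincide. The list therefore makes sense only for the 5×5 residual covariance R. If the intercept stays, the total covariance is V = R + τ²J, where J is a matrix of ones.

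**Step 2: redundancy.** V has 5 × 6 / 2 = 15 distinct elements. The rank of the derivative of V with respect to its parameters shows how many parameters the data can separate.

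| Structure | Parameters alone | With intercept | Rank with intercept | Redundant | Depends on lobe order |
|---|---|---|---|---|---|
| UN | 15 | 16 | 15 | 1 | no |
| CS | 2 | 3 | 2 | 1 | no |
| VC | 1 | 2 | 2 | 0 | no |
| CSH | 6 | 7 | 7 | 0 | no |
| TOEP | 5 | 6 | 5 | 1 | yes |
| TOEPH | 9 | 10 | 10 | 0 | yes |
| AR(1) | 2 | 3 | 3 | 0 | yes |
| ARH(1) | 6 | 7 | 7 | 0 | yes |

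The algebra agrees. Under CS the common covariance c and τ² enter only as c + τ². Under TOEP, τ² is added to each of the five bands and is absorbed by them. UN absorbs it in the same way. Without the intercept, UN has 15 parameters and rank 15.

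**Step 3: order.** Under AR(1) the correlation between positions i and j is ρ^|i−j|. In the protocol's listing RUL is first and LUL is fourth, giving ρ³. Numbered RUL, LUL, RML, RLL, LLL, the same pair has ρ. With an assumed ρ of 0.5 these are 0.125 and 0.5. Keeping the intercept does not remove this, because τ² + σ²ρ^|i−j| still varies with the lag unless ρ = 0. Reversing a list leaves |i−j| unchanged, so there are 5!/2 = 60 distinct orders.

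**Step 4: does AIC selection change with order?** There were 24 simulated datasets per scenario, n = 34, and each was fitted under all 60 orders (24 × 60 = 1,440 selections). Assumptions: Gaussian changes, lobe means only, no baseline covariate, no random intercept, TOEPH not fitted.

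- *Correlation 0.5 within and 0.2 between lungs, SDs 0.6 to 1.3.* The selected structure changed with order in 24 of 24 datasets. The median AIC range across orders was 26.7 for AR(1) and 30.5 for ARH(1). An ordered structure won 264 + 9 = 273 of 1,440 selections (19%), but 13 of 24 (54%) in the protocol's own order.
- *Equal correlation 0.35, equal SDs.* The selection changed in 16 of 24 datasets. The median AIC ranges were 19.5 and 20.5. An ordered structure won 135 + 61 + 6 = 202 of 1,440 (14%), and 5 of 24 (21%) in the protocol's order.

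**Step 5: effect on the planned output.** In a smaller check (six datasets, n = 34, within-lung clustering, unequal SDs, a subset of the structures), the choice changed with order in all six and the per-lobe standard errors shifted by up to about 7% to 13%.

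**The case against.** The case for leaving the text alone is substantial.

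- *The fallback may never be used.* True. The order problem arises only if UN fails to converge.
- *The natural codings agree.* True. The protocol's listing is the exact reverse of alphabetical order, and reversal leaves the AR(1) and Toeplitz fits unchanged. The risk lies in other numberings, or in missing lobe rows shifting positions when no lobe index is declared. Agreement between two codings does not, however, give the lag a meaning.
- *The random effect may be meant to be replaced.* Possible. UN alone is then identifiable and the redundancy disappears. The addendum does not say so, and under that reading the ordered structures remain in the list.

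Three stronger readings are tempting, and the documents do not support them.

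- *A reader might infer that standard errors are materially understated.* If lobes are equally correlated at 0.2, 0.4 or 0.6, the best-fitting AR(1) gives a standard error for the across-lobe mean that is 0.874, 0.853 or 0.877 of the true one. With the patient intercept kept, the ratio is 1.000 in all three cases, because intercept plus AR(1) contains compound symmetry. Without the intercept, AIC must still prefer AR(1) to CS, which happened in 16%, 2% and 0.3% of simulated datasets. The across-lobe mean is also not a planned output.
- *A reader might infer that the Hessian check removes the sensible structures and leaves the ordered ones.* The table shows otherwise. VC and CSH keep full rank with the intercept, and ordered TOEP is among the redundant structures.
- *A reader might object to one structure serving every endpoint*: "This is the structure that will then be used for the rest of the analysis of lobe dependency models". That is a prespecified simplification that limits discretion, and no harm from it has been shown.

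**Conclusion.** The point holds as a minor specification defect. Four of the seven fallback structures depend on an order that the lobes do not have. Read together with the patient random effect, UN, CS and TOEP are each over-parameterised by one. The second part rests on reading Addendum 2.9 with SAP 3.2.1.5. That is the natural reading, but it is an inference, and whether UN replaces or supplements the intercept is left open.

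Redundancy makes a failed fit or a singular Hessian more likely, not certain. It is also unclear whether the Hessian check applies to UN or only to the fallback list.

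The simulated frequencies and the 7% to 13% shift in per-lobe standard errors rest on assumed covariances and on models without the patient intercept. They show that the effect can occur, not how large it is in this trial. Only the secondary lobe-level mixed models are touched. The primary paired t-test on total mucus volume uses no lobe covariance.

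**What to change.** Reword Addendum 2.9 as follows.

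1. State that UN is the residual covariance across the five lobes within a patient and is fitted without the patient random intercept. Nothing is lost, since a 5×5 unstructured matrix already contains the pattern that the intercept would produce.
2. If UN fails, use CSH, and if that fails, CS. CS is equivalent to a random intercept plus VC when the shared correlation is non-negative. Both structures are unchanged by relabelling.
3. Delete TOEP, TOEPH, AR(1) and ARH(1).
4. Say whether the positive-definite Hessian check also applies to UN, and point the cross-reference to SAP 3.2.1.5 and 3.2.2.5.

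The cost is a few lines of text and a shorter list of models to fit. No extra data or analysis is needed.

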2.11 Mucus Volume

Mucus volume hasn't previously been presented on previous studies the way it is here. As a result, the rules outlined in the SAP aren't quite appropriate for this parameter. Below are details specific to mucus volume that will be followed when presenting data related to mucus volume.

2.11.1 Summary Statistics

In section 3.1.1 of the SAP, it outlined decimal place rules for continuous data that are based around the number of decimal places that appear in the data. Mucus volume is outlined in the data to up to 9 decimal places. Therefore, the current decimal place rules aren't quite appropriate to follow when summarising this parameter.

For mucus volume data, all summary statistics will be rounded to 4 decimal places.

2.11.2 Regression Coefficients

The regression coefficient precision that is outlined above in section 2.8.2 is not appropriate for mucus volume as some of the detail is lost when rounding to 2dp. Therefore, the regression coefficient for mucus volume will be rounded to 3dp.

2.11.3 Skewed Data

Mucus volume data that is skewed would be log-transformed according to SAP section 3.2.1. This data can be zero however, so a log plus one transformation will be used if needed. That is, each value of the data will be increased by one and then the log-transformation will be applied. The Skewness of the data is determined by checking box plots of the data and seeing if the mean deviates from the median greatly and if there is asymmetry between the quartiles.

Specific airway volume and airway wall volume are the only other FRI parameters that need to be considered for possible transformation. Should it be determined that a transformation is required the rules in SAP section 3.2.1 should be followed.

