3.2.2.3 Handling of Dropouts and Missing Data

The analysis populations will only include participants who have completed three doses of study intervention and have baseline and post-benralizumab treatment study evaluation (PROs, CT scans, and spirometry tests). To that end, participants withdrawing before Week 13 and participants with one of the two FRI measurements missing will not be included in the analysis.

3.2.2.4 Primary Analysis of Secondary Endpoint 1

For each secondary FRI endpoint listed in Table 2, a paired t-test will be used to assess whether there is a statistically significant difference in the mean value at Week 0 versus Week 13, without adjustments for participant characteristics. Data will be log-transformed prior to analysis if there is evidence of skewness.

3.2.2.5 Secondary Analysis of Secondary Endpoint 1

For the secondary analysis of the secondary endpoint, a mixed-effects model will be employed to incorporate the repeated measurements (corresponding to the different lobes) for each subject. The fitted model will be provide estimates of the average percent change from baseline per lobe, with lobe as a fixed effect and a patient-level random effect to estimate the heterogeneity across lobes. The model will adjust for the baseline value of the secondary endpoint. The model will take the same form as described in Equation 1, but with "mucus volume" replaced by the secondary outcome of interest.

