1.4 FRI Parameters

Two secondary FRI parameters that are outlined in the protocol will be replaced by new ones in the final analysis. The two that are set to be replaced are listed below:

Developed from TP-BPM-WW-032; related to SOP-BPM-WW-001 D3250R00107

Statistical Analysis Plan Addendum

Parameter from Protocol	Description	Parameter from data transfer	Anticipated Data Selection Specifications
Trimmed distal specific siVaw at TLC (secondary)	Specific airway volume		
Trimmed distal specific siVaw at FRC (secondary)	Specific airway volume		

Table 2 Functional Respiratory Imaging Parameters (old)

They will be replaced by the following:

Tabla ²	3 Functio	nal Dasnir	otory Ime	aging Dara	motors (now)
I abic .	5 Functio	паі ксэрп	atory mil	aging 1 al a	meters (new)

Parameter from Protocol	Description	Parameter from data transfer	Anticipated Data Selection Specifications
Untrimmed distal iVaw at TLC (secondary)	Airway volume	-CCI	
Untrimmed distal iVaw at FRC (secondary)	Airway volume		

The rationale for this change is that there have been more and more insights in the mode of action of biologics in severe asthma. These compounds have greater effects on airway recruitment that can be related to reduced mucus plugging and decreased airway inflammation. In the past, FRI has been used in multiple studies evaluating the effects of inhaled medication in asthma, which

were used as a base when developing this protocol initially several years ago. Those compounds led to greater reductions in airway constriction, which would mostly be relevant when looking at trimmed airways, but more evidence became available that a reduction in bronchoconstriction is not the main driver for biologics. By focusing on the absolute airway volumes from untrimmed airway models there is greater understanding of the effects related to the airways opening up and bringing them within scan resolution after treatment.

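### SAP Addendum 2.11.3 still ties the skewness rule to specific airway volume, which Addendum 1.4 dropped, so the two airway volume endpoints that replaced it get no skewness check

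*SAP*

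**What the plan says.** SAP section 3 says in general terms that FRI parameters may be log-transformed to reduce skewness. SAP 3.2.2.4 then assigns a paired t-test to each secondary FRI endpoint in SAP Table 2 and adds: "Data will be log-transformed prior to analysis if there is evidence of skewness". No secondary FRI endpoint is left out.

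Addendum 2.11.3, in the part of the Addendum that lists changes to the SAP, does two things. For mucus volume it sets out how skewness is judged (box plots, mean against median, asymmetry of the quartiles) and deals with zeros: "This data can be zero however, so a log plus one transformation will be used if needed". For everything else it closes the list: "Specific airway volume and airway wall volume are the only other FRI parameters that need to be considered for possible transformation". For those two it adds: "Should it be determined that a transformation is required the rules in SAP section 3.2.1 should be followed". SAP 3.2.1.4 provides a plain log.

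Addendum 1.4 changes the endpoints themselves: "Two secondary FRI parameters that are outlined in the protocol will be replaced by new ones in the final analysis". Its Table 2 lists the ones removed, trimmed distal siVaw at TLC and at FRC, both described as specific airway volume. Its Table 3 lists the ones brought in, untrimmed distal iVaw at TLC and at FRC, both described as airway volume.

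**The concern.** The two Addendum sections do not fit together. The eligibility list in 2.11.3 uses the name of a parameter that 1.4 removes, and its closed wording shuts out the parameters that 1.4 adds. An analyst who follows the text checks nothing for iVaw and tests it on the raw scale.

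The sponsor evidently thought airway volume might need transforming, since siVaw was one of only two parameters kept on the list. Nothing in the Addendum says why the untrimmed absolute volume should need the check less. If the raw values are right-skewed, a few participants with large airway volumes dominate the mean and variance of the differences, and power is lost. If the analyst instead assumes that iVaw inherits the siVaw rule, the scale of two secondary endpoints becomes a choice made at analysis. Addendum 2.14 shows that a dry run has already been made.

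**Working it through.** **Step 1: which parameters the rule reaches.** The visible FRI parameters in SAP Table 2 are mucus volume, mucus plugs score, air trapping at FRC, airway wall volume (iVaww) at TLC, siVaw at TLC, siVaw at FRC, lung volume (iVlung) at TLC and iVlung at FRC: eight in all. Part of the list is blacked out, so the counts cover visible parameters only.

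| Rule applied to | Eligible for transformation | Count |
|---|---|---|
| SAP section 3 and 3.2.2.4, SAP Table 2 set | all | 8 of 8 |
| Addendum 2.11.3, same set | mucus volume, iVaww, siVaw at TLC, siVaw at FRC | 4 of 8 |
| Addendum 2.11.3, set after Addendum 1.4 | mucus volume, iVaww | 2 of 8 |

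The drop from 4 to 2 is the two iVaw endpoints. It comes only from the mismatch between 1.4 and 2.11.3. The other four parameters not covered (plugs score, air trapping, iVlung at TLC and at FRC) are left out by the list itself.

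**Step 2: what this could cost for iVaw.** The plan gives no figure to reproduce: the basis of the sample size is redacted and no distribution of iVaw is reported. The calculation below is an illustration.

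From the protocol synopsis and SAP section 3: n = 29 in the primary analysis population, two-sided 5% level. Assumed: log volume is normal between participants with SD 0.3 to 0.7; independent noise at each visit has SD σ = 0.15 to 0.25 on the log scale; volume rises by 15%.

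On the log scale the between-participant SD cancels, and the standardised effect is d = ln(1.15) / (σ√2), with ln(1.15) = 0.1398.

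- σ = 0.15: d = 0.1398 / 0.2121 = 0.659; power of the paired t-test with 28 degrees of freedom = 93%.
- σ = 0.25: d = 0.1398 / 0.3536 = 0.395; power = 54%.

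On the raw scale each difference is the participant's own volume level times a noise term, so spread between participants inflates the variance. Simulation with 20,000 trials per cell gives:

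| σ | Between-participant log-SD | Raw power | Log power |
|---|---|---|---|
| 0.15 | 0.3 | 90% | 93% |
| 0.15 | 0.5 | 86% | 93% |
| 0.15 | 0.7 | 78% | 93% |
| 0.25 | 0.3 | 49% | 54% |
| 0.25 | 0.5 | 44% | 54% |
| 0.25 | 0.7 | 38% | 54% |

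A separate set of runs put the raw range at 39 to 90%, which agrees to within a point. With no change, the raw test rejects 4.3 to 4.8% of the time and the log test 4.8 to 5.0%.

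**Step 3: the mucus plugs score.** Protocol 8.1.1.2 describes two scores: a sum of plug counts over segments, with no upper limit, and a present-or-absent score per segment summed to 0 to 20. Neither document says which one is the secondary endpoint. The choice decides whether a log helps. Assume a median of 4 plugs, log-SD 1.2, 20% with none, visit noise 0.5, a 40% fall and n = 29. For the count, power is 39% raw and 56% on log(x+1). For the 0 to 20 score from the same model, with plugs spread evenly over 20 segments, it is 55% raw and 50% on log(x+1). Raw was ahead for the 0 to 20 score in all five settings tried.

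**The case against.** Four arguments can be made against the point.

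First, this looks like an editing slip. The revision history dates the FRI parameter change to Addendum version 2.1, so 2.11.3 is plausibly text left over from before it. SAP section 3 also still allows transformation of FRI parameters in general. That explains the conflict but does not settle it: 2.11.3 is the later and more specific rule, and its list is closed.

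Second, the simulation favours the log by construction, because effect and noise are both multiplicative. That stands. The figures show what could be lost if iVaw behaves this way, not what will be.

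Third, the check looks at the distribution of values, while a paired t-test depends on the differences. That also stands as a weakness of the SAP rule. It is no reason to apply the rule to a dropped endpoint and not to its replacement.

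Fourth, leaving out the plugs score, air trapping and lung volume may be deliberate. It may be, and for these three the text contains no contradiction, only a narrowing without a stated reason.

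A reader might also infer more than the documents support. One might say that the plugs score is bound to lose power on the raw scale. Step 3 shows that this holds for the unbounded count and reverses for the 0 to 20 score. One might treat the plugs score as the main support for the primary endpoint, but the secondary endpoints carry no ranking and SAP 2.3.4 sets no multiplicity procedure. One might call the raw test invalid, but in these settings it is at worst slightly conservative.

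**Conclusion.** Addendum 2.11.3 is wrong as written for airway volume. It keeps a skewness rule for two endpoints that are no longer in the final analysis and withholds from their two replacements a check that SAP 3.2.2.4 gave every secondary FRI endpoint. This follows from the text alone.

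The size is uncertain. Under the assumptions in step 2, the raw test gives up about 3 points of power at the low end of spread and noise (90 against 93%) and about 15 at the high end (39 against 54%). If iVaw is not skewed, nothing is lost.

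The gap for the plugs score is a question for the sponsor, not an established loss. The matter is worth correcting but minor: it affects secondary endpoints, does not inflate false positives and leaves the primary analysis as it is.

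**What to change.** In Addendum 2.11.3, replace specific airway volume with untrimmed distal airway volume (iVaw) at TLC and FRC. Keep airway wall volume and the reference to SAP 3.2.1.

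State which of the two scores in protocol 8.1.1.2 is the total mucus plugs score. If it is the unbounded count, give it the same skewness check and log(x+1) rule as mucus volume, because a plain log is undefined at zero. If it is the 0 to 20 score, do not impose log(x+1), since it can lower power. If air trapping and lung volume are meant to stay off the list, say why.

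The cost is a sentence or two of Addendum wording and box plots for two more parameters. Any endpoint that is transformed would be reported as a ratio, with raw summaries still shown. The change should be dated and made before the final analysis, so that the scale is fixed by the plan.
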